10.3 Access to Individual Subject Treatment Assignments by Amgen or Designees

Blinded individuals will not have access to unblinded information until the study is formally unblinded. Unblinding and potentially unblinding information should not be distributed to the study team, investigators or subjects prior to the study being formally unblinded (eg, the formal unblinding may occur at the final analysis rather than during the primary analysis) except as specified (eg, [Section 10.4.1](#) and [Section 9.2.2.2](#)).

10.4 Planned Analyses

10.4.1 Interim Analyses

[Table 12](#). specifies the timing of planned phase 3 analyses for CMR and OS.

Approved

Table 12. Timing of the Planned Phase 3 Analyses for Complete Metabolic Response and Overall Survival

Analysis Number	Analysis Time Since First Subject Randomized ^a (months)	Primary Endpoint: CMR	Key Secondary Endpoint: OS
1	8	Interim for futility (25% of subjects complete treatment and tumor assessment, ~10 weeks after randomization)	-
2	13	Interim for futility (50% of subjects complete treatment and tumor assessment, ~10 weeks after randomization)	-
3	18	Interim for efficacy, futility (75% subjects complete treatment and tumor assessment, ~10 weeks after randomization) and sample size re-estimation.	Interim for efficacy and sample size re-estimation (~153 events, ~65% of the total)
4	23	Final	-
5	26	-	Final (236 events)

CMR=complete metabolic response; DMC=data monitoring committee; OS=overall survival

^a Time by which the required number of subjects will have had the opportunity to be assessed for the CMR endpoint. Actual DMC analysis may occur up to 2 months later.

Based on the conditional power at the third interim analysis of CMR and first interim analysis of OS, there will be a possibility to increase the sample size by at most 50% using the method of [Gao, Ware and Mehta \(2008\)](#), which will be described in detail in the statistical analysis plan. The sample size will be increased if either CMR or OS interim results are in the pre-specified promising zone. If the sample size is increased due to only OS results being in the promising zone, then the primary CMR analysis will occur as scheduled once 296 subjects have been assessed for CMR.

The interim futility boundaries will use the Lan-DeMets alpha-spending approach to non-binding O'Brien-Fleming boundaries.

Table 13. Futility Stopping Rules for Complete Metabolic Response

Analysis Number	Information Fraction	Number of Analyzed Subjects	Number of Randomized Subjects*	Futility Boundary (Z Scale)	Cumulative Beta Spent
1	25%	74	111	-1.313	0.001
2	50%	148	185	0.368	0.020
3	75%	222	259	1.307	0.058
4	100%	296	296	2.012	0.100

* Includes additional subjects randomized during the 10 weeks required prior to the response assessment

Approved

Table 14. Efficacy Stopping Rules for Complete Metabolic Response

Analysis Number	Information Fraction	Number of Analyzed Subjects	Number of Randomized Subjects*	Efficacy Boundary (Z Scale)	Cumulative Alpha Spent
3	75%	222	259	2.340	0.010
4	100%	296	296	2.012	0.025

* Includes additional subjects randomized during the 10 weeks required prior to the response assessment

Table 15. Efficacy Stopping Rules for Overall Survival

Analysis Number	Information Fraction ^a	Number of Events ^a	Number of Randomized Subjects ^b	Efficacy Boundary (p-Value Scale)	Cumulative Alpha Spent
3	65%	153	258	0.005	0.005
5	100%	236	296	0.023	0.025

^a Estimated. Analysis Number 3 will occur at the same time as the analysis for complete response

^b The number of subjects is calculated based on the case that the study is not stopped early. The sample size can be increased by up to 50% and applies to all of the above tables

The data monitoring committee (DMC) will make recommendations regarding study continuation and sample size re-estimation based on interim analysis results.

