7.2.8 End of Study

Study completion will occur once 236 death events for phase 3 subjects have occurred or 12 months after the last subject in phase 3 is randomized if 236th death in phase 3 subjects is not observed.

If the study will not continue for the phase 3 portion, the study will conclude when all phase 2 subjects have had the opportunity to complete long term follow-up as described above.

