10.2 Sample Size Considerations

10.2.1 Phase 2

The sample size for the phase 2 part of the study is determined by a 1-sample test of the rate of CMR **during the first 12 weeks** after **initiation** of blinatumomab. With the 1-sided type I error rate (α) set at 0.025, a null hypothesis response probability (π_0) of 15%, and an alternative response probability (π_1) of 40%, a sample size of 36 subjects will provide 90% power to reject the null hypothesis that the response probability is no more than 15%. Being able to make this determination will represent evidence of clinical activity and warrant advancement into the phase 3 part of the study.

10.2.2 Phase 3

The primary endpoint is CMR. A CMR rate of 22% in the IC arm vs. 40% in the blinatumomab arm is hypothesized. The odds ratio of CMR rate will be tested at the 1-sided significance level of 0.025. With these assumptions and a 1:1 randomization

ratio, a sample size of 296 subjects will provide 89% power. The sample size is adjusted for 3 interim futility analyses when 25%, 50%, and 75% of the subjects have had the opportunity to complete the tumor assessment and 1 interim efficacy analysis when 75% of the subjects have had the opportunity to complete the tumor assessment. The interim futility boundaries will use a Lan-DeMets beta-spending approach to an O'Brien-Fleming boundary and the interim efficacy boundaries will use a Lan-DeMets alpha-spending approach to an O'Brien-Fleming boundary. The details of these interim analyses are specified in the [Section 10.4.1](#).

Overall survival is a key secondary endpoint and the study is also powered for overall survival. If the null hypothesis for the primary endpoint is rejected, then OS will also be tested at a 1-sided significance level of 0.025. Assuming the true hazard ratio is 0.65 a final OS analysis after 236 death events will provide 90% power. With a median survival time of 4.4 months in the IC arm vs. 6.7 months in blinatumomab arm, accrual rates of 14.5 subjects per month, a 5% drop-out rate per year, and a targeted sample size of 296 randomized subjects, it is estimated that the 236th event will occur within 26 months of the start of randomization.

Sample size re-estimation will be allowed at an interim analysis (see [Section 10.4.1](#)).

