10.4.4 Final Analysis

The final analysis will test whether OS is superior in the group randomized to blinatumomab compared to the group randomized to IC. The final analysis will be triggered by the date when the 236th death in phase 3 subjects is reported in the clinical trial database, or the study duration reaches 12 months from the last subject randomized. The estimated time is 26 months to reach the OS event goal. Barring a sample-size increase, since the enrollment period is expected to last 21 months, the estimated maximum follow up time is 33 months.

In case that the phase 3 portion of the study is not initiated, the final analysis will occur when all subjects in phase 2 complete long term follow-up defined in [Section 7.2.7](#).

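### Phase 3 sample-size re-estimation gives no revised OS death target: subjects can rise by up to 50%, but the OS and study-completion triggers still name the 236th death, and Table 15 footnote b points the other way

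*Protocol*

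**What the plan says.** **The adaptation.** At analysis 3 (about 153 deaths, month 18 in Table 12), section 10.4.1 allows at most 50% more subjects, so 296 can become up to 444: "The sample size will be increased if either CMR or OS interim results are in the pre-specified promising zone". If only OS is promising, the one stated consequence is that CMR is still analysed at 296 subjects. Nothing is said about the number of deaths.

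**The triggers.** Section 10.4.4 states: "The final analysis will be triggered by the date when the 236th death in phase 3 subjects is reported in the clinical trial database", or 12 months after the last randomisation. Section 7.2.8 states: "Study completion will occur once 236 death events for phase 3 subjects have occurred". The synopsis, the glossary, 3.5.2, 7.2.7 and the OS test in 10.5.3 use the same count. The caveats about a sample-size increase in 10.4.3 and 10.4.4 qualify estimated times, not the count.

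**Text pointing the other way.** Table 15 footnote b reads: "The sample size can be increased by up to 50% and applies to all of the above tables". Table 15 is where the death counts stand. Footnote a to that table calls the counts estimated, and one sentence in 3.5.2 gives 236 as approximate.

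**The SAP.** Section 10.4.1 leaves the method to the SAP. The supplied SAP is a phase 2 plan and marks interim analysis as not applicable (sections 7.9 and 8).

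**The concern.** The information in a log-rank test comes from deaths. Extra subjects help only if they produce extra deaths before the analysis. If OS is still tested at 236 deaths, enlarging the sample brings that analysis forward and leaves its power where it was, so an increase made because OS looked promising would not serve its purpose.

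The second problem is order. Section 10.5.1 tests CMR first and OS only if CMR succeeds. If a CMR-driven increase keeps accrual open while study completion stays tied to the 236th death, the OS trigger can be reached before the enlarged CMR sample has been assessed, or even enrolled.

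Both bear on the primary and key secondary tests. They need to be settled before anyone sees unblinded interim data.

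**Working it through.** **Inputs (protocol 10.2.2 and Table 12).** OS is tested at one-sided 0.025. On OS power the plan says: "Assuming the true hazard ratio is 0.65 a final OS analysis after 236 death events will provide 90% power". The timing inputs are medians of 4.4 months (IC) and 6.7 months (blinatumomab), accrual of 14.5 per month, 5% drop-out per year, 296 subjects, 1:1 allocation, and an OS interim at about 153 deaths.

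**1. Reproducing the plan.**
- Power at 236 deaths and hazard ratio 0.65: √236/2 × |ln 0.65| = 3.309, and Φ(3.309 − 1.960) = 91.1%. Allowing for the interim look it is 90.9%. The plan states 90%.
- Expected deaths by month T, summed over the two arms: (14.5/2) × λ/(λ+η) × ∫[1 − exp(−(λ+η)(T−s))] ds, for s from 0 to the smaller of T and N/14.5. Here λ = ln 2/4.4 = 0.1575 or ln 2/6.7 = 0.1035 per month, and η = −ln(0.95)/12 = 0.0043.
- With N = 296 the 153rd death falls at month 17.8 (plan: 18) and the 236th at month 25.7 (plan: 26).

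**2. OS-driven increase, triggers read literally.** Let θ = −ln(interim hazard ratio), I₁ = 153/4 = 38.25, I₂ = deaths/4, and final critical value c = 1.99. Conditional power under the current trend is Φ[(θI₂ − c√I₂)/√(I₂ − I₁)]. The interim hazard ratios are illustrative assumptions, because the promising zone is not defined in the documents. The 354 is 236 × 1.5, which applies the cap on subjects to deaths.

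| Interim HR | 236 deaths (I₂ = 59) | 354 deaths (I₂ = 88.5) |
|---|---|---|
| 0.78 (θ = 0.2485) | (14.66 − 15.29)/4.555 = −0.14, about 45% | (21.99 − 18.72)/7.089 = 0.46, 68% |
| 0.75 (θ = 0.2877) | (16.97 − 15.29)/4.555 = 0.37, 64% | (25.46 − 18.72)/7.089 = 0.95, 83% |

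The number of subjects does not enter the formula. At 236 deaths these values are the same for 296 subjects as for 444.

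**3. Timing when accrual continues at 14.5 per month.** Twelve weeks is 84/30.44 = 2.76 months.

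| N | Enrolment ends (N/14.5) | Last 12-week assessment | 236th death |
|---|---|---|---|
| 296 | 20.4 | 23.2 | 25.7 |
| 317 | 21.9 | 24.6 | 24.6 |
| 320 | 22.1 | 24.8 | 24.5 |
| 340 | 23.4 | 26.2 | 24.2 |
| 350 | 24.1 | 26.9 | 24.1 |
| 444 | 30.6 | 33.4 | 24.1 |

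- Above about 317 subjects (317/296 = 1.07) the 236th death comes before the last CMR assessment.
- Above about 350 (350/296 = 1.18) it comes before enrolment ends.
- At the maximum of 444, about 350 would be randomised at the 236th death, which is 94 subjects and about 6.5 months short.

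Sensitivity of the 350 figure, on ranges I assumed: 334 to 366 for accrual of 12 to 17 per month, and 330 to 372 if both arms had a median of 4.4 months or both had 6.7.

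**4. If deaths were scaled as well.** 354 deaths from 444 subjects would be expected at month 33.2. That is after enrolment ends (30.6) and inside the 12-month limit (30.6 + 12 = 42.6).

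**The case against.** Four points can fairly be made in the plan's favour.

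- **The trigger numbers may be base-case values.** The 296-subject CMR trigger in 10.4.3 is as unqualified as the 236. Yet 10.4.1 implies that it moves after a CMR-driven increase, since it holds 296 in place only when OS alone is promising. If both are read literally, CMR is analysed at about month 23 (Table 12), before the 236th death at month 24.1 or later, and the testing order holds. This stands: the order problem arises only if CMR is analysed on the enlarged sample while 236 stays fixed.
- **Footnote b may scale the deaths.** A reader might infer that the protocol plainly fixes OS at 236 whatever happens to the sample. Footnote b, with the estimated and approximate counts, prevents that conclusion. But the footnote speaks of sample size, hangs on the subjects column and gives no new count. If it does scale the deaths, it contradicts 7.2.8, 10.4.4 and 10.5.3.
- **The detail was left to the SAP.** True, but the supplied SAP does not contain it, and the completion rule is a protocol rule.
- **Phase 3 is conditional.** Section 3.5.2 makes it depend on the phase 2 data, and no phase 2 analysis is touched. This lowers the priority but leaves the conflict in place.

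**Conclusion.** The point holds as an unresolved conflict: subjects can be increased, no revised death target is stated, and the operative OS and completion triggers name 236 deaths. Following those triggers, an OS-driven increase leaves conditional power at about 45% or 64% in the two illustrative cases, where 354 deaths would give 68% or 83%. Its only effect on OS is to move the 236th death from about month 25.7 to as early as month 24.1. The order and enrolment problems begin at increases of about 7% and 18%, and only if CMR is analysed on the enlarged sample.

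Two stronger inferences are not supported. One is that the 236th death always ends the study before an enlarged sample is enrolled: at 320 or 340 subjects enrolment finishes first. The other is that 148 extra subjects (444 − 296) would be exposed without gain in OS power: under the literal rule and the plan's own rates the study stops at about 350, or some 54 extra.

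The timings rest on the protocol's medians, accrual and drop-out with exponential survival and uniform accrual. The conditional powers rest on the assumed interim hazard ratios and an unadjusted final statistic; the cited re-estimation method may change the critical value. The matter arises only if phase 3 opens and analysis 3 leads to an increase.

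**What to change.** Before any phase 3 randomisation:

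1. In 10.4.1 and Table 15, define the OS re-estimation in deaths, from 236 up to a stated maximum (354 if the 50% cap is applied to deaths), with subjects added to reach it. State the final critical value according to the cited re-estimation method.
2. In the synopsis, glossary, 3.5.2, 7.2.7, 7.2.8, 10.4.4 and 10.5.3, replace the fixed 236th death with the target number of deaths: 236, or as re-estimated at analysis 3.
3. Make the 296-subject CMR trigger (synopsis, 3.5.2, 10.4.3) conditional in the same way.
4. State that the final OS analysis and study completion may not precede the final CMR analysis.
5. Reword Table 15 footnote b so that it says which columns change.

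The cost is protocol wording. If the maximum increase were used, the OS readout would come at about month 33 instead of month 26.

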10.4.2 Data Monitoring Committee

An external independent DMC will oversee the interim analyses. In addition, the DMC will assess safety approximately every 6 months provided enrollment is adequate. The timing of safety reviews may be adjusted in order to coincide with scheduled DMC interim analyses for futility and efficacy. On the basis of their reviews, the DMC will make recommendations to Amgen regarding the continuation of the study and sample size re-estimation of the study. The DMC will consist of 3 or more members including 2 or more clinicians with relevant specialties and 1 or more statisticians. The DMC will be supported by an external independent statistician who is responsible for preparing reports that describe the ongoing clinical study data. Details regarding the responsibilities of the DMC and the independent statistician will be described in the DMC Charter.

10.4.3 Primary Analysis

Phase 2: The primary analysis will report the CMR rate among blinatumomab treated subjects.

Phase 3: The primary analysis will test whether CMR/OS is superior in the group randomized to blinatumomab compared to the group randomized to IC. The primary analysis will be triggered by the date when 296 subjects have had the opportunity to

complete at least 1 tumor assessment. Barring a sample-size increase, the estimated time of this analysis is 21 months after the first subject is randomized.

10.4.4 Final Analysis

The final analysis will test whether OS is superior in the group randomized to blinatumomab compared to the group randomized to IC. The final analysis will be triggered by the date when the 236th death in phase 3 subjects is reported in the clinical trial database, or the study duration reaches 12 months from the last subject randomized. The estimated time is 26 months to reach the OS event goal. Barring a sample-size increase, since the enrollment period is expected to last 21 months, the estimated maximum follow up time is 33 months.

In case that the phase 3 portion of the study is not initiated, the final analysis will occur when all subjects in phase 2 complete long term follow-up defined in [Section 7.2.7](#).

10.5 Planned Methods of Analysis

10.5.1 General Considerations

Continuous variables will be summarized by the non-missing sample size (n), mean, standard deviation, median, first and third quartiles, minimum, and maximum.

Categorical variables will be summarized by the n and percentage in each category.

Time to event endpoints will be summarized with hazard ratios, Kaplan-Meier (KM) curves, KM proportions at select time points, KM quartiles (when estimable), the number of subjects with events, the number of subjects censored, and the pattern of censoring.

Point estimates for efficacy endpoints will be accompanied by 2-sided 95% confidence intervals including estimates of KM quartiles ([Brookmeyer and Crowley, 1982](#)), KM proportions ([Kalbfleisch and Prentice, 1980](#)), and binomial proportions ([Clopper CJ and Pearson, 1934](#)).

The phase 3 study will have an overall alpha of 0.025 with 1-sided testing. To preserve the overall significance level, statistical testing of the primary and key secondary endpoint will follow a hierarchical structure. First, CMR rate will be tested. If the blinatumomab arm demonstrates superiority over the IC arm for CMR, then OS will be tested.

Approved

10.5.2 Primary Efficacy Endpoint

Phase 2:

The percentage of subjects with a CMR **during the first 12 weeks** after **initiation** of blinatumomab will be summarized with an exact binomial 95% confidence interval.

Summary of CMR during the treatment will also be provided.

Phase 3:

A 1-sided Cochran-Mantel-Haensel test, which will adjust for the stratification factors at randomization, will be used to determine if the blinatumomab arm has a significantly higher CMR rate compared to the IC arm. In addition, the percentage of subjects in each treatment arm with a CMR will be summarized with an exact binomial 95% confidence interval. Subjects missing post-baseline disease assessments will be considered not to have achieved CMR.

10.5.3 Secondary Efficacy Endpoint(s)

Phase 2:

Other secondary efficacy endpoints include OR after **initiation** of blinatumomab and during the treatment, PFS, duration of CMR, DOR, successful mobilization rate, alloHSCT rate, autoHSCT rate and 100-day NRM after autoHSCT.

OR **during the first 12 weeks after initiation of** blinatumomab during the treatment will be summarized with an exact binomial 95% confidence interval.

PFS will be summarized with the KM summaries.

Duration of CMR and duration of response will be summarized with the KM summaries in Responders Analysis Set.

Successful mobilization rate, autoHSCT rate and alloHSCT rate will be summarized with an exact binomial 95% confidence interval. AutoHSCT rate will be analyzed using autoHSCT Analysis Set.

The 100-day NRM after autoHSCT rate will be summarized with the cumulative incidence function with **relapse or deaths due to relapse** treated as competing risks. For this endpoint, time to non-relapse deaths will be measured starting from the date of autologous HSCT.

Phase 3:

OS is the key secondary efficacy endpoint for Phase 3. A 1-sided stratified log-rank test, stratified by the randomization factors, will be used to determine if OS is superior in the

blinatumomab arm compared to IC arm when the 236th death in phase 3 subjects is reported. In addition, a hazard ratio with a 2-sided 95% confidence interval will be estimated from a stratified Cox regression model. The KM summaries will be performed by treatment group.

Other secondary efficacy endpoints include OR, PFS, duration of CMR and ORR, successful mobilization rate, HSCT rate, 100-day NRM after HSCT rate. Overall response rate will be summarized by treatment group with an exact binomial 95% confidence interval. For descriptive purposes, a 1-sided Cochran-Mantel-Haenszel test, which will adjust for the stratification factors at randomization, will test if the blinatumomab arm has a higher ORR compared to the IC arm. PFS, duration of CMR and the duration of ORR will be summarized with the KM summaries by treatment group. For descriptive purposes, a stratified log-rank test, stratified by the randomization factors, will be provided. A hazard ratio with a 2-sided 95% confidence interval will be estimated from a stratified Cox regression model.

Successful mobilization rate and HSCT rate will be summarized by treatment group with an exact binomial 95% confidence interval.

The 100-day NRM after autologous HSCT rate will be summarized with the cumulative incidence function with non-relapse deaths treated as competing risks by treatment group. For this endpoint, time to non-relapse deaths will be measured starting from the date of autologous HSCT.

